4.2 Scientific Rationale for Study Design

The European Medicine Agency’s “Guideline on strategies to identify and mitigate risks for first-in-human (FIH) clinical trials with investigational medicinal products; (EMEA/CHMP/SWP/28367/07 Rev 1)”, is intended to assist Sponsors in the transition from nonclinical to early clinical development. It outlines factors influencing risk to be considered in the nonclinical testing strategy and designs of FIH clinical studies or investigational medicinal products. This guideline applies to all new chemical and biological investigational medicinal products except gene and cell therapy products. This guideline also applies to relevant Clinical Trial Authorization applications submitted in accordance with Directive 2001/20/EC (EU No 536/2014).

The study is designed in 2 stages to allow for the evaluation of the vaccine safety and immunogenicity across 2 geographic locations. This allows an assessment of the vaccine in both low and high endemicity settings and evaluate the potential impact of environmental exposure on the vaccine immune response. The first stage of the trial

which is the First Time in Human part of the trial is designed with the required safety measures to serve as risk mitigation (refer to Section 2.3.2). The vaccination schedule is selected based on the number of doses expected to be immunogenic in the target population for primary immunization with the vaccine if eventually licensed (ie, young infants from 6 weeks of age). The specific time points are selected to allow integration with existing Expanded Programme on Immunization schedules in the target regions for the vaccine (ie, 6 weeks, 14 weeks, and 9 months of age). Evaluating the safety of three doses in adults will allow the eventual testing of the same number of doses in the target population.

4.2.1 Choice of Comparator Vaccines

For the adults in Europe, a placebo will be used. The placebo will be the diluent for the study intervention (iNTS-TCV and iNTS-GMMA) to obtain the low dose. It has been used in past GVGH-managed trials and in many licensed vaccines without any safety concerns. For the population in Europe, it is important to compare the reactogenicity of the candidate vaccine against a placebo to objectively assess its safety profile.

A saline solution is used in this study to ensure adequate blinding and to also ensure an appropriate comparison of the study arms based on the effects of the vaccine components (all participants to receive an equal amount of alum).

For the adults in Stage 2 in Africa, Menveo and Boostrix have been used as comparators in a previous study conducted in Kenya during the development of the *S. Sonnei* 1790GAHB vaccine [Obiero, 2017]. Menveo is indicated for active immunization to prevent invasive meningococcal disease caused by *Neisseria meningitidis* serogroups A, C, Y and W-135. The vaccine contains no preservative or adjuvant. Meningitis being prevalent in Malawi, administering a dose of Menveo will provide some benefits to the participants. Boostrix provides protection against tetanus, diphtheria, and pertussis. It can be administered as a booster in this age population. Typhim Vi is licensed for the prevention of typhoid fever in individuals from 2 years of age, however it is also not routinely administered to adults in Malawi. In the typhoid-endemic region of Malawi, providing a dose of Typhim Vi will provide some benefits to the participants.

The separate administration of the iNTS-GMMA and TCV vaccines as comparators is to allow for the evaluation of the vaccines' immunogenicity as a combination (trivalent) vaccine and as separate vaccines, evaluate the likelihood of interference of iNTS-GMMA with the immunogenicity of TCV vaccines, and vice versa, and aid the planning of future development of either a combination trivalent vaccine or a bivalent iNTS-GMMA vaccine.

4.2.2 Rationale for Blinding

Because of the difference in the presentation of the investigational vaccine and the comparator vaccines, ie, the difference in the labeling of the vaccine vials and the difference in the appearance of the diluent presentation, double blinding is not possible. The study will be conducted in an observer-blind manner. Refer to the definitions of double blinding and observer-blind in [Appendix 1](#) and refer to Section [6.3.3](#) for details.

When all data up to Day 85 in Stage 2 are available, a group-unblinded interim statistical analysis for immunogenicity will be performed. This analysis may lead to the unblinding of the study team with respect to some participants. A statistician will be unblinded for the analysis.

The remaining study personnel will stay blinded until study end (Day 337 in Stage 2). The Investigator and the participants will not have access to the treatment allocation up to study end (Day 337 in Stage 2).

4.3 Justification for Dose

- In preclinical studies, [CCI](#) [REDACTED]
[REDACTED] The TCV component of the vaccine is already licensed by Biological E with good immunogenicity demonstrated in populations aged 6 months to 64 years. [CCI](#) [REDACTED]
[REDACTED] There was also no signal of interference between the different components of the vaccine in the animal experiments.
- The highest dose of the iNTS-TCV vaccine to be used in this trial was tested in a repeated-dose toxicology study in rabbits and it concluded that based on the findings from the study, 4 IM administrations of the vaccine at 2-week intervals to New Zealand White rabbits were well tolerated with no evidence of systemic toxicity. Additionally, the vaccine-related changes were mild in severity and likely represented a physiological reaction following the immune stimulation in response to the vaccine candidate.

Lower starting doses will be used for the first stage of the trial before escalating to the full dose to mitigate any potential risks related to dose increases.

The selected full dose of the TCV component is the dose of the licensed TCV vaccine, while the full dose of both iNTS components have been tested in repeat-dose toxicology studies in rabbits and were well tolerated. Two doses will be tested, [CCI](#) [REDACTED] dilutions of the full doses (low dose) of all study interventions and the full doses of all the study interventions. The licensed TCV is 25 µg in 0.5 mL dose and in the absence of a commercial diluent, it is most feasible to achieve the fractional low dose of [CCI](#) mL, [CCI](#) [REDACTED]

CC1 [REDACTED]. The selected low dose will be used as a safety lead-in before testing the full dose in the FIH stage of this trial and will allow an initial assessment of the vaccine immunogenicity using a lower antigen content. The alum component is the same as has been tested in previous trials with GMMA vaccines and will be the same irrespective of the dose-level.

4.4 End of Study Definition

A participant is considered to have completed the study if he/she returns for the last visit/contact or is available for the last scheduled procedure/contact as described in the protocol.

The end of study (EoS) is defined as the date of the Last Subject Last Visit (LSLV) or date of last testing results released, whichever comes last. In the latter, EoS must be achieved no later than 8 months after LSLV.

4.5 Study Holding Criteria

4.5.1 Study Holding Rules

Holding rules will be introduced to ensure a well-controlled exposure to the investigational candidate vaccine and to prevent participants from being exposed to any unnecessary safety risks in this FIH study. The holding rules will point attention to safety signals and indicate requirements for formal committee reviews that will decide whether additional participants can be exposed to the study intervention if particular criteria are met. Study holding rules are defined in [Table 5](#).

Holding rule 1 and 2c (threshold ≥ 1) will be assessed by the Investigator on a continuous basis irrespective of the number of enrolled participants and meeting any of these holding rules will trigger a hold of study intervention administration irrespective of number of enrolled participants and/or timing of the event relative to study intervention administration. Holding rule 2 (2a-b) and 1d.2 in Stage 2 (threshold ≥ 2) will be assessed during the safety evaluations on blinded or unblinded data.

These holding rules have been written under the assumption that the safety data from all participants will be available. If the data from some participants are not available (eg, in case a participant is lost to follow-up), then the holding rules will be assessed on a pro-rata basis.

If the Investigator becomes aware of a holding rule being met, he/she must suspend administration of the study intervention and inform the Sponsor's delegate immediately (holding rules 1a-d and 2c).

However, for the other holding rules (1d.2 in Stage 2, 2a and 2b) which have a threshold ≥ 2 , the Investigator will inform the Sponsor's delegate immediately, without suspending the administration of the study intervention.

The Sponsor's delegate will inform the Investigator if holding rules 1d.2 in Stage 2 and 2a-b are met.

The following communication sequence must be followed:

- The concerned site staff has to put study intervention administration on hold.
- The concerned site staff must immediately inform IQVIA CRA and Medical Monitor (contact details will be provided in a separate document) via email and phone communication who will in-turn inform the GVGH Study Responsible Project Physician.
- All informed site staff will confirm to their local contact that action has been taken providing appropriate documentation to GVGH through the IQVIA CRA and Medical Monitor.
- GSK will further evaluate the case with the iSRC and GSK Global Safety Board and will take the decision to stop or to restart the study intervention administration. GVGH project physician will inform the IQVIA project lead of the decision and the rationale for the decision and all site staff will be informed about that final decision by IQVIA project lead.

Table 5 Study Holding Rules

Events	Number or % of participants needed to pause administration of study intervention	
	Stage 1 Step 1 and Step 2	Stage 2
1a Death or any life-threatening SAE regardless of causality	≥1	≥1
1b Any non-life-threatening SAE that cannot be reasonably attributed to another cause other than study intervention administration	≥1	≥1
1c Any withdrawal from the study (by Investigator or participant request) following a Grade 3 AE that cannot be reasonably attributed to another cause other than study intervention administration	≥1	≥1
1d.1 Any administration site or general solicited event leading to hospitalization, OR Necrosis at the injection site, each within the 7-day (Days 1 to 7) post-administration period	≥1	≥1
1d.2 Fever >40°C (104°F) within the 7-day (Days 1 to 7) post-administration period	≥1	≥2
2a Any Grade 3 solicited administration site event (lasting 48 h or more) in an investigational group, within the 7-day (Days 1 to 7) post-administration period	≥2	NA
2b Any Grade 3 solicited general AE (lasting 48 h or more) in an investigational group, within the 7-day (Days 1 to 7) post-administration period	≥2	NA
2c Any Grade 3 unsolicited AE in an investigational group, that can be reasonably attributed to the study intervention administration, within the 7-day (Days 1 to 7) post-administration period or Any Grade 3 abnormality in prespecified hematological or biochemical laboratory parameters in an investigational group within the 7-day (Days 1 to 7) post-administration period	≥1	NA

Abbreviations: AE = adverse event; h = hours; SAE = serious adverse event; NA = not applicable

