- With 45 participants in administration cohort, holding rule 1d.2 has more than 80% chance of not being met for study intervention administration with a true incidence rate below 2% and has more than 60% chance of being met with a true incidence rate above 4.4%.

Figure 4 Unblinded Review: Safety Holding Rules 2a and 2b After 4 and 16 Participants

[figure not shown]

Figure 4 illustrates the following:

- With 4 participants in administration cohort, each holding rule 2a and 2b has more than 90% chance of not being met for study intervention administration with a true incidence rate below 14% and has more than 69% chance of being met for study intervention administration with a true incidence rate above 50%.
- With 16 participants in administration cohort, each holding rule 2a and 2b has more than 90% chance of not being met for study intervention administration with a true incidence rate below 3% and has more than 61% chance of being met for study intervention administration with a true incidence rate above 12.5%.

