In Step 2, a second sentinel of 10 participants vaccinated on consecutive days. They will receive a phone call for safety surveillance on the day following the first study intervention administration (Day 2), before proceeding with study intervention administration in the subsequent participants. The remaining 30 participants will be vaccinated at least 60 minutes apart.

Likewise, in Stage 2, the first 21 participants will receive the study interventions sequentially, at least 60 minutes apart, with a safety phone call/home Visit the day after administration for safety surveillance.

All 155 participants in the study (Stage 1 and Stage 2) will be closely monitored at the site for at least 60 minutes post-administration for safety surveillance.

Seven days after the first study intervention administration in the low dose cohort (Step 1) in Stage 1 is completed, an iSRC will receive a summary of all available safety data (solicited administration site events and systemic events, unsolicited AEs and SAEs) and listings of hematology and blood chemistry test values obtained following the first study intervention administration (baseline and 7 days after study intervention administration). Based on evaluation of the safety data (review #1, [Table 14](#)), the iSRC will make a recommendation, as to whether the next stage of the trial (Stage 1/Step 2), when the administration of the full dose of the study interventions to the study participants, should start.

Seven days after all participants in Stage 1/Step 1 have received their second study intervention, there will be an iSRC review of all safety data collected up to day 7 after second administration (Day 64) in Step 1 (review #2, [Table 14](#)). If there is no safety concern with any of the investigational groups, the second study intervention administration in Stage 1/Step 2 can commence.

There will be another iSRC data review 28 days after the second administration in Stage 1/Step 2 (review #3, [Table 14](#)). In the case of a favorable review, recruitment of participants in Stage 2 in Africa can commence.

All the participants in Stage 1 will complete the trial according to the schedule. A final safety evaluation of all data collected in Stage 1 will be performed once the study is completed.

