The first 21 participants in Stage 2 will receive the study interventions sequentially, 60 minutes apart, with a follow-up safety phone call/home Visit conducted one day after the first administration to identify any safety concerns in the participants who received the study interventions. The Investigator will proceed with study interventions administration in the subsequent study participant only in the case that there is no safety concern in the previous participant who received the study interventions. If the Investigator becomes aware of a holding rule being met, he/she must suspend administration of the study intervention and inform the Sponsor's delegate immediately.

Seven days after the first administration of the study interventions of the first 21 participants in Stage 2, there will be an iSRC to review all available safety data collected (review #4, [Table 14](#)). Following this, in the event of a positive safety review, the 84 remaining participants will receive the study interventions in parallel.

A last iSRC review analysis for safety will be performed 28 days after second administration in the first 21 participants in Stage 2 to allow the third study intervention administration of all participants in Stage 2 and to support preparation for future studies (review #5, [Table 14](#)).

A summary of the planned unblinded iSRC reviews for the trial are presented in [Table 14](#). In case of any safety concerns, ad hoc iSRC reviews may be called.

Instream blinded monitoring will also be performed by the internal GSK Safety Review Team (SRT); details of these blinded data reviews for the trial are presented in [Table 15](#).

Table 14 Summary of the iSRC Reviews*

iSRC #	Timing of Safety Evaluation	Subsequent Activities
1	7 days after first administration with low dose of 10 sentinel participants in Step 1 (Stage 1)	First administration with full dose of 40 participants in Step 2 (Stage 1)
2	7 days after second administration with low dose of 10 sentinel participants in Step 1 (Stage 1)	Second administration with full dose of 40 participants in Step 2 (Stage 1)
3	28 days after second administration with full dose of 40 participants in Step 2 (Stage 1)	First administration with full dose of first 21 participants in Stage 2
4	7 days after first administration of first 21 participants in Stage 2	First administration of remaining 84 participants in Stage 2

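### Stage 1 Step 2: neither review table lists a check of holding rules 2a/2b between the 10 full-dose sentinels and the other 30, and dosing continues until the delegate replies, with no time limit

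*Protocol*

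**What the plan says.** Step 2 (Protocol 4.1.1 and 9.7) gives the first full dose to 10 sentinels, one per day, each with a safety call the next day. Then: "The remaining 30 participants will be vaccinated at least 60 minutes apart".

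Table 5 sets the Stage 1 threshold at two or more for rules 2a and 2b. Rule 2a reads "Any Grade 3 solicited administration site event (lasting 48 h or more) in an investigational group", within Days 1 to 7; rule 2b is the same for general events. Section 4.5.1 treats these two rules differently from the rest in Stage 1:

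- Rules 1a-d and 2c are assessed continuously by the Investigator, and one case stops dosing.
- Rules 2a/2b "will be assessed during the safety evaluations on blinded or unblinded data". The Investigator reports at once, "without suspending the administration of the study intervention". Any reply comes back from the delegate, who "will inform the Investigator if holding rules 1d.2 in Stage 2 and 2a-b are met". No time is given for that assessment or reply.

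The scheduled evaluations are in Section 9.7:

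- **Table 14.** Review #1 uses 7-day low-dose data from Step 1 and releases the first full dose for all 40 Step 2 participants. Review #2 follows the second low dose and releases the second full dose. Review #3 comes 28 days after the second full dose.
- **Table 15.** Stage 1 has blinded looks covering all subjects to 7 days after each vaccination. There is no row for the sentinels.

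An ad hoc iSRC review may be called for safety concerns (Synopsis and 9.7). Sections 4.1.1 and 9.7 also tell the Investigator, without excluding any rule, to suspend on learning that a holding rule is met.

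**The concern.** The sentinels are the safeguard for the first full doses in a first-in-human stage. For severe but non-hospitalized reactogenicity, such as prolonged Grade 3 pain, swelling, headache or fatigue, rules 2a/2b are the only count-based stop. Nothing listed ensures that the sentinels are counted against them before 30 more people are dosed.

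The Day 2 call comes about 24 hours after dosing, so it cannot confirm a 48-hour event. The next planned contact is a diary reminder, allowed 1 to 3 days after dosing (Table 2), and diaries are transcribed at the Day 8 visit (Table 1). A blinded Investigator also cannot tell whether two events belong to the same group.

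The instructions pull apart as well. Section 4.5.1 exempts 2a/2b from suspension by the Investigator, while 4.1.1 and 9.7 do not. A site that follows 4.5.1 could keep giving full doses after two sentinels in one group have met the rule.

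**Working it through.** **1. The plan's own figure.** Figure 4 is titled for "Safety Holding Rules 2a and 2b After 4 and 16 Participants". Using P(X ≥ 2) = 1 − (1−p)^n − np(1−p)^(n−1):

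| n per group | True rate | Computed | Stated |
|---|---|---|---|
| 4 | 14% | 0.903 not met | over 90% |
| 4 | 50% | 0.688 met | over 69% (rounding) |
| 16 | 3% | 0.918 not met | over 90% |
| 16 | 12.5% | 0.612 met | over 61% |

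The figure reproduces. Sixteen is the whole full-dose group. Four is the Step 1 group size, and also the expected number of Step 2 sentinels per investigational group if 2:2:1 holds within the first 10 (assumed). No listed review is tied to those four.

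**2. Calendar at the fastest pace** (sentinel k dosed on day k, participant 11 on day 11; assumed).

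- The Day 8 visit of sentinel k falls on day k + 7. By day 11 this covers k ≤ 4, so 4 of 10 sentinels (3 if that day's own visit is not counted). Sentinel 10 is seen on day 17.
- By elapsed time, 9 of 10 sentinels are at least 48 h past dosing on day 11 (11 − k ≥ 2), and 8 of 10 at least 72 h.
- At 5 doses a day (assumed), the other 30 take 6 days and finish on day 16. At 3 a day, 6 × 3 = 18 are dosed by day 16.
- The 30 split 12:12:6 under 2:2:1, so 24 are active.
- Counting instead from the first Step 1 dose, participant 11 is dosed on day 10 + 7 + 1 + 10 = 28 at the earliest. Review #2 falls between day 10 + 52 + 7 = 69 and day 10 + 62 + 7 = 79. It could precede participant 11 only if Step 2 ran slowly, and nothing ties it to that point.

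**3. Chance that the sentinels already meet one rule.** Per group, P(X ≥ 2 | n = 4) = P. For either of two groups, 1 − (1 − P)². Expected events among the 24 are 24p; multiplying by the either-group chance gives an upper bound on events avoided.

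| True rate p | P | Either group | 24p | Upper bound avoided |
|---|---|---|---|---|
| 10% | 0.052 | 0.102 | 2.4 | 0.2 |
| 25% | 0.262 | 0.455 | 6 | 2.7 |
| 50% | 0.688 | 0.902 | 12 | 10.8 |

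**4. A pooled blinded trigger at two events**, with 8 active sentinels and no placebo events. It fires with P(X ≥ 2 | n = 8). It is not a breach when there is exactly one event in each group, P(X = 1 | n = 4)².

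| True rate | Fires, per class | One event per group | Share of firings not a breach |
|---|---|---|---|
| 3% | 0.022 | 0.012 | 54% |
| 10% | 0.187 | 0.085 | 45% |
| 14% | 0.311 | 0.127 | 41% |
| 25% | 0.633 | 0.178 | 28% |

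These shares apply to a count after all 8 have finished follow-up. If the pause comes at the second event itself, the two events lie in different groups with probability 4/7 = 57%.

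**The case against.** The best defence is that 2a/2b already have continuous cover. The Investigator must report at once, the delegate must say if the rule is met, and an ad hoc iSRC can be called at any time. Complaints at the sentinel call are evaluated against the holding rules before the next participant is dosed. Not suspending for a single event follows from the threshold of two and the blind. This stands: what is missing is a scheduled check, a time limit and a pause while the count is made.

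A reader might infer that the sponsor requires a gate in Stage 2 and forgot it here, since review #4 takes place "7 days after first administration of first 21 participants in Stage 2" and before the other 84. The documents do not support that. Table 5 marks 2a/2b as not applicable in Stage 2, and those 21 start on hourly spacing rather than one per day. Review #4 is not a direct comparator.

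A reader might also take 2.7 or 10.8 avoidable events as the expected harm. Those need true rates of 25% or 50%, which nothing in the documents supports, and an off-schedule route that never acts. At 10% the upper bound is 0.2. Nor does 4 of 10 mean that the site knows nothing about the other six: it counts Day 8 diary visits, and severe reactions may be known earlier by phone.

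Finally, Section 9.7 says planned reviews also appear in Figure 1, and the SAP (4.1, 4.2) defers details to the iSRC charter. Neither is visible here, and either may add a step.

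**Conclusion.** The point holds in a narrow form. On the two review tables, no evaluation of 2a/2b falls between the full-dose sentinels and the other 30. Section 4.5.1 lets dosing run until an untimed reply arrives, and 4.1.1 and 9.7 can be read the other way.

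It does not follow that the sentinel step lacks a stop. Hospitalization for a solicited event, injection-site necrosis, fever above 40°C, related SAEs and related Grade 3 unsolicited AEs each stop dosing at one case, and review #2 precedes the second full dose.

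The size depends on an unknown event rate: a 10% chance at a 10% rate, and 45% at 25%, that a given rule is met in either group among the sentinels, assuming four per group. How many of the 30 are dosed before the sentinels' diaries are in depends on the site's pace.

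This is an inexpensive improvement, with medium confidence. The summary of changes for the current amendment refers to deviations already seen in Stage 1, so first full doses in Step 2 may be complete. If so, the dosing change comes too late for this trial.

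**What to change.** In 4.5.1, cross-referenced from 4.1.1 and 9.7:

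- After a single 2a/2b event, report it and keep dosing, as now.
- Once two participants, pooled and blinded, have a Grade 3 solicited event of the same class (administration site or general) lasting 48 h or more, pause dosing until the delegate or an ad hoc unblinded iSRC confirms the count by group.
- Before participant 11 of Step 2, document a blinded check of the sentinel diary data against this trigger.

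This also settles which suspension instruction governs 2a/2b.

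**Cost.** A short pause when the trigger fires: among the sentinels, about 19% per class at a 10% true rate and 2% at 3%, with roughly half of those firings not a breach. Placebo events would add false firings.

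**Fuller, optional version.** Wait for every sentinel's Day 8 visit. Participant 11 then moves from day 11 to day 18, or to day 21 at the end of the 7-10 day visit window, so 7 to 10 days. Review #3 and the start of Stage 2 move with it. This needs no new data and no new body.

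**Intermediate version.** Fix the reminder call at Day 4 with a scripted question on Grade 3 events and their duration. Sentinel 10 is then called on day 13 and participant 11 dosed on day 14, about 3 days later. It adds data collection and misses later-onset events.
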